4.3 Study Duration

The duration of individual subject participation ranges from 12 to 16 weeks depending on the subject's cohort and arm assignments. Table 4 presents the estimated duration of subject participation accounting for time needed to complete eligibility screening, autologous plasma collection(s), FDP manufacturing, and the infusion and follow-up visits.

Table 4. Duration of Subject Participation by Cohort and Treatment Arm

Cohort, Treatment Arm	Screening Period	WB/Plasma Collection Time	FDP Manufacturing Time	Planned Study Follow-up Period	Total Expected Duration
Cohort 1, Arm 1	~2 Weeks	1 Week	~5 Weeks	4 Weeks	~12 Weeks
Cohort 1, Arm 2		1 Week			~12 Weeks
Cohort 2, Arm 3		~5 Weeks			~16 Weeks
Cohort 2, Arm 4		1 Week			~12 Weeks
Cohort 3, Arm 5		~3 Weeks		6 Weeks	~16 Weeks
Cohort 3, Arm 6		~3 Weeks			~16 Weeks

4.4 Data Handling Conventions

4.4.1 Non-Analyzable Data

Non-analyzable data will include inconclusive, invalid laboratory values, and data resulting from deviations in performing study procedures (i.e. data sent to the wrong laboratory or resulting from errors in procedure or processing). The protocol's Study Events Schedule indicates the specific time window in which each of the visits is to occur post-infusion. Results outside of these visit windows will be included in the analysis. Both non-analyzable data and results outside of visit windows will be treated as deviations and documented in the final clinical study report.

4.4.2 Baseline Values

Baseline demographic variables are those captured at the Screening Visit. Safety endpoint values, vital signs and laboratory test results, taken at the Infusion Visit just prior to subject infusion, are the baseline values.

4.4.3 Repeated Data

In cases where measurements taken at specific time-points must be repeated for any reason (e.g., the result of the initial laboratory test clinically or procedurally requires that it be repeated), only the initial or original value will be considered. However, all data, original or repeat, will be presented in the data listings.

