#### **Estimated Number of Subjects to Screen: 48**

#### Maximum Number of Subjects to Enroll: 24

Cohort 1, Arm 1: (n=4) subjects are to be infused with 1 autologous FDP unit (FDP-CPD) manufactured from WB-derived FFP.

Cohort 1, Arm 2: (n=4) subjects are to be infused with 1 autologous FDP unit (FDP-ACD) manufactured from FFP collected via plasmapheresis.

Cohort 2. Arm 3: (n=4) subjects are to be infused with 2 autologous FDP (FDP-CPD) units manufactured from WB-derived FFP.

Cohort 2, Arm 4: (n=4) subjects are to be infused with 2 autologous FDP units (FDP-ACD) manufactured from FFP collected via plasmapheresis.

Both arms of Cohort 3 are to be infused with 3 units of autologous plasma product at each of 2 infusion visits. Infusion visits are to be scheduled such that there is a period of no less than 2 weeks between infusions.

Cohort 3, Arm 5: (n=4) subjects will receive 3 autologous FDP units (FDP-ACD) manufactured from FFP collected via plasmapheresis at their first infusion visit followed by infusion with 3 autologous FFP units, collected via plasmapheresis, at their second visit.

Cohort 3, Arm 6: (n=4) subjects will be infused with these products in the opposite order as Arm 5 (eg, autologous FFP at first infusion and autologous FDP-ACD at the second).

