4.4.4 Missing Data

Counts of missing data will be included with the summary descriptive statistics.

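### SAP 4.4.3 keeps the original value for every repeated test, so a procedurally invalid original cannot be replaced by its valid repeat

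*SAP*

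**What the plan says.** SAP 4.4.3 (Repeated Data) sets one rule for all repeats. Its example is the case where "the result of the initial laboratory test clinically or procedurally requires that it be repeated", so procedural causes are covered explicitly. In every such case "only the initial or original value will be considered". The repeat is kept for display only: "However, all data, original or repeat, will be presented in the data listings". Listing 34 shows original and repeat side by side, and footnotes to the laboratory listings say that the original is the one shown.

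SAP 4.4.1 says: "Non-analyzable data will include inconclusive, invalid laboratory values, and data resulting from deviations in performing study procedures". Its examples include samples sent to the wrong laboratory and processing errors. It goes on: "Both non-analyzable data and results outside of visit windows will be treated as deviations and documented in the final clinical study report". It says that out-of-window results are included in the analysis. It does not say outright that non-analyzable values are left out, and it does not mention replacing them.

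Two neighbouring rules matter. SAP 4.4.2 says that pre-infusion safety values "taken at the Infusion Visit just prior to subject infusion, are the baseline values". SAP 4.4.4 says: "Counts of missing data will be included with the summary descriptive statistics". Protocol 11.5 adds no replacement rule.

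**The concern.** A procedurally required repeat exists because something went wrong with the first measurement. The originals that 4.4.3 tells the analyst to keep in that situation are therefore the ones that 4.4.1 calls non-analyzable. The two sections conflict, and neither way of resolving them uses the valid measurement.

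At stake are the laboratory and vital-sign summaries: Tables 9-13 and Figures 3-4, all in population S3. The groups are very small. Table 11 is also sensitive to a single result, because it classifies each subject on the maximum (or minimum) post-infusion value. For PT, INR and aPTT, high means a rise of at least 20% from the pre-infusion value. An error in that pre-infusion value carries into every comparison made against it: a falsely low one can make sound later results look high, and a falsely high one can hide a real rise.

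**Working it through.** No figure in the plan depends on this rule, so there is none to reproduce. The check sets the sections side by side and then sizes each reading.

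**Inputs**
- Subjects per arm: 4 (SAP Table 1; Protocol synopsis). Per cohort: 8 (SAP 3.4).
- Population for Tables 9-13 and Figures 3-4: S3 (SAP 4.2.2).
- Table 11 rows: one per treatment, produced separately for Infusion #1 and Infusion #2 in Cohort 3, with no total row. The planned row size is therefore 4. The denominator is limited to subjects with a normal pre-infusion value and at least one post-infusion value.
- Displays that can pool 8 subjects: the Table 12 total rows, and Figure 3, which is titled by product.
- Size of the error: not in the documents. Assumed k = 2, 3 or 5 between-subject SDs.

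**Reading A: 4.4.1 removes the invalid original, and 4.4.3 still bars the repeat**
- Share of the group lost = 1/n. For n = 4 this is 25%, leaving 3 of 4. For n = 8 it is 12.5%, leaving 7 of 8.
- Standard error multiplier at the same SD = √(n/(n−1)). For n = 4, √(4/3) = 1.15. For n = 8, √(8/7) = 1.07.
- If the lost value is the pre-infusion one, the subject has no change score for that analyte and infusion. In the Table 9 and Table 12 shells that means two scores (30 minutes and 4 hours) for most analytes, three for hematology (24 hours added), and one for analytes measured only at 30 minutes. The subject also drops out of the Table 11 denominator.

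**Reading B: 4.4.3 governs, and the invalid original is summarised**
- Table 11: one spurious post-infusion value can turn 0/4 into 1/4, which is 25 percentage points with all four subjects in the denominator.
- Mean: shift = k/n SD.
- Expected sample variance = σ²[1 + k²(1 − 1/n)/(n − 1)] = σ²(1 + k²/n), so the SD is inflated by about √(1 + k²/n).

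| k (assumed) | Mean shift, n = 4 | SD inflation, n = 4 | Mean shift, n = 8 | SD inflation, n = 8 |
|---|---|---|---|---|
| 2 | 0.50 SD | 1.41 | 0.25 SD | 1.22 |
| 3 | 0.75 SD | 1.80 | 0.375 SD | 1.46 |
| 5 | 1.25 SD | 2.69 | 0.625 SD | 2.03 |

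The n = 8 columns apply only to the pooled displays named above.

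**If a valid repeat replaced the invalid original:** the group keeps all its subjects, the shift from the error is 0, and no change score is lost.

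**The case against.** The strongest reply is that the rule has a sound purpose and a small reach.

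- **Purpose.** Keeping the original prevents unwelcome results from being replaced selectively. This stands for repeats that confirm a clinically abnormal but valid result, which is the only laboratory-repeat reason that Protocol 8.5 gives for an unscheduled visit. It does not cover procedural repeats, which 4.4.3 names.
- **Which reading applies.** By stating that out-of-window results are included, 4.4.1 implies that non-analyzable values are not. This stands. A reader might infer that invalid values will necessarily be analysed, but the documents point more towards Reading A. The mean shifts and the false high are conditional on the less likely reading.
- **Is there a usable repeat?** The baseline is drawn just before infusion, and the post-infusion draws have windows of ±5 and ±40 minutes (Protocol 8.2). A redraw prompted by an error found later cannot stand for those time points. This stands in part: a re-run of the same sample, or a redraw caught in time, can.
- **Reach.** Protocol 6.1 bases the safety conclusions on TEAEs only. The DSMB package in SAP 4.5.3 is Tables 1.1-8.3 (without 7.4-7.6) and Figures 1-2. No hypothesis is tested, medians and quartiles are reported, and both values are listed. All of this stands, so a reader should not infer that the primary endpoint or the planned DSMB tables are compromised.
- **Crossover pairs.** A reader might infer that a lost baseline cuts the FDP-FFP pairs from 8 to 7. Within-subject comparison is a stated purpose of Cohort 3, but no planned table computes a paired difference or has a pair count. Nor does any Table 11 row hold 8 subjects, so a 12.5-point shift in that table matches no planned output.

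**Conclusion.** The concern holds in limited form. As written, 4.4.3 conflicts with 4.4.1 for procedurally invalid originals, and following the plan either discards a valid result or summarises an invalid one. The likelier cost is a lost time point: one of four subjects in an arm or shift-table row, or all change scores for one analyte and infusion when the baseline is the value lost. The less likely cost is up to 25 points in a Table 11 row, or k/4 SD in an arm mean.

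These sizes are per event. They rest on the planned group sizes, on a valid repeat being available, and, for the means, on an assumed k. The documents give neither an error size nor a frequency of procedural repeats, though a dedicated listing shows that repeats are expected. The effect is confined to descriptive laboratory and vital-sign summaries. The change should be made because it is a stated rule with a worse result than an easy alternative, not because the trial's main conclusions are at risk.

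**What to change.** Amend SAP 4.4.3 along these lines:

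> Section 4.4.1 takes precedence over this section, and the first analyzable result for the time point is used: if the original is classed as non-analyzable, a valid repeat for the same time point replaces it, either a re-run of the same sample or a redraw that still represents that time point (for baseline, before the infusion starts). Repeats done to confirm a valid but clinically abnormal result do not replace the original.

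The classification should be made by blinded staff before unblinding and without reference to the size of the value. SAP 3.3.1 already keeps the Data Manager and Project Statistician blinded. The condition should be that the repeat represents the same time point, not that it falls inside the visit window, because 4.4.1 includes out-of-window results. Keep both values in Listing 34.

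The cost is two sentences in the SAP and a flag in the laboratory dataset. Protection against selective repeats is kept.

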4.4.4 Missing Data

Counts of missing data will be included with the summary descriptive statistics.

4.5 Statistical Methods and Analysis

4.5.1 Overview and General Plans

This section describes the analytic approach for addressing each of the study's objectives by the defined primary and secondary endpoints. The analysis will be descriptive and consist of frequencies and percentages for categorical measures and the number of subjects, mean, standard deviation, median, minimum, maximum, 25th and 75th percentile for continuous measures as appropriate. Descriptive statistics will be summarized for each treatment group. SAS Version 9.3 or higher (SAS Institute Inc., Cary, NC) will be used to perform all statistical analyses.

Modeling

Modeling is not incorporated in the SAP since it is not required to meet the primary or secondary objectives.

Multiplicity Issues

Not powered to test for treatment group differences; no adjustment for multiple testing is planned for the study analyses.

Project Center Effects

This is a single-site study. Adjustment for project center effects will not be performed.

Interim Analysis

No interim analyses are planned for this study.

4.5.2 Summarize and Characterize Consented Subjects and Enrolled Subjects

Subjects must provide written informed consent if they are willing to participate in the study. However, they only will be enrolled if eligibility is confirmed by responses to the screening questionnaires and results from their physical examination and laboratory tests. For this analysis, the number of subjects screened will be equal to the number of subjects with a date of providing written informed consent. The number of enrolled subjects will equal the number of subjects that have a date of enrollment.

Subject disposition will be displayed in consort diagrams (Figures 1 and 2) that will exhibit the number of subjects across all cohorts and study arms who were: screened, enrolled, assigned or randomized to treatment, infused (received treatment) and discontinued.

Descriptive analyses conducted on enrolled subjects will include: demographics and physical characteristics at entry.

Definitions for Cohorts 1 and 2

The following definitions will generate Figure 1:

- Subjects screened: the total number of subjects with a date of informed consent.
- Subjects discontinued prior to enrollment (i.e., screen failures): the total number of subjects with a date of informed consent minus the total number of subjects with a date of enrollment.
- Reasons subjects discontinued prior to enrollment: any inclusion criteria not met or exclusion criteria met.
- Subjects enrolled/treatment assigned: the total number of subjects with a date of enrollment.
- Subjects discontinued after enrollment but prior to infusion: the total number of subjects with a date of enrollment minus the total number of subjects who received any plasma infusions (Exit Interview CRF).
- Subjects infused: the total number of subjects who did receive any plasma infusions during the study (Exit Interview CRF).
- Subjects discontinued on or after infusion: the total number of subjects infused minus the total number of subjects with a status of 'Completed' (Exit Interview CRF) in each treatment arm.
- Reasons subjects discontinued on or after infusion: the subject's status on the Exit Interview CRF.
- Subjects completed: the total number of subjects with a status of 'Completed' on the Exit Interview CRF in each treatment arm.

Definitions for Cohort 3

The following definitions will generate Figure 2:

- Subjects screened: total number of subjects with a date of informed consent.
- Subjects discontinued prior to enrollment (i.e., screen failures): the total number of subjects with a date of informed consent minus the total number of subjects with a date of enrollment.
- Reasons subjects discontinued prior to enrollment: any inclusion criteria that was not met or exclusion criteria that was met.
- Subjects enrolled: the total number of subjects with a date of enrollment.
- Subjects discontinued after enrollment but prior to randomization: the total number of subjects with a date of enrollment minus the total number of subjects with a date of randomization.
- Reasons subjects discontinued prior to randomization: the subject's status on the Exit Interview CRF for the subjects in the previous bullet.
- Subjects randomized: the total number of subjects with a randomization date.
- Subjects discontinued after randomization but prior to infusion #1 visit: the total number of subjects with a date of randomization minus the total number of subjects with a visit date on the Infusion Form.
- Reasons subjects discontinued after randomization but prior to infusion #1 visit: the subject's status on the Exit Interview CRF for the subjects that meet the criteria in the previous bullet.
- Subjects enter infusion #1 visit: the total number of subjects with a visit date on the Infusion Form.
- Subjects discontinued after entering the infusion #1 visit but prior to receiving infusion #1: the total number of subjects with a visit date on the Infusion Form minus the number of subjects that receive any plasma infusions during the study (Exit Interview CRF).

- Reasons subjects discontinued after entering the infusion #1 visit but prior to receiving infusion #1: the subject's status on the Exit Interview CRF for the subjects that meet the criteria in the previous bullet.
- Subjects receive infusion #1: the number of subjects who did receive any plasma infusions during the study (Exit Interview CRF).
- Subjects discontinued on or after receiving infusion #1 but prior to receiving infusion #2: the number of subjects who received infusion #1 minus the number of subjects with a start date of infusion #2 (Infusion CRF) and > 0 mL administered in each treatment arm.
- Reasons subjects discontinued on or after receiving infusion #1 but prior to receiving infusion #2: the subject's status on the Exit Interview CRF for the subjects that meet the criteria in the previous bullet.
- Subjects receive infusion #2: number of subjects with a start date of infusion #2 (Infusion CRF) and > 0 mL administered in each treatment arm.
- Subjects discontinued on or after infusion #2: the number of subjects who received infusion #2 minus the total number of subjects who had a status of 'Completed' on the Exit Interview CRF in each treatment arm.
- Reasons subjects discontinued on or after infusion #2: the subject's status on the Exit Interview CRF for the subjects that meet the criteria in the previous bullet.
- Subjects completed: the total number of subjects with a status of 'Completed' (Exit Interview CRF) in each treatment arm.

4.5.3 Conduct Safety Analyses (Primary Objective)

To provide the DSMB with formal safety reports for review, analyses required to generate Table 1.1 – Table 8.3 and Figures 1 and 2 will be conducted as prescribed in the FDP-1 DSMB Charter, except for Tables 7.4-7.6. For Cohort 3, Open and Closed session tables will be created. The Open session tables will present overall totals for Cohort 3. The Closed session tables will present the data by masked treatment arm (A or B).

Safety data will be summarized for each cohort using standard descriptive statistics.

- For quantitative variables, the following statistics will be provided:
 - Number of subjects;
 - Mean;
 - Standard deviation, minimum, maximum;
 - Median; and
 - 25th and 75th percentile.
- For categorical variables, percentages will be calculated using the number of subjects with non-missing data for the specific variable.

AEs will be coded using the most recent version of the Medical Dictionary of Regulatory Activities preferred terms and will be grouped by system, organ, and class designation. AEs will be summarized using standard FDA-recommended templates distinguishing those defined as TEAEs. A TEAE will be defined as an AE that emerges during or following treatment (infusion), having been absent pretreatment. For all TEAEs, relatedness to infused product will be presented. TEAEs related to study treatment will be defined as definitely or probably related to study treatment. A SUSAR will be defined as a Suspected, Unexpected, Serious Adverse Reaction. A listing of SUSARs will be provided by USAMMDA upon reconciliation of their SAE database with the Oracle Clinical database.

Use of the Centers for Disease Control National Healthcare Safety Network Hemovigilance Module criteria will ensure consistent definitions are applied when using transfusion-related event terms, such as

transfusion related acute lung injury or transfusion associated circulatory overload. The National Cancer Institute Common Terminology Criteria will be used to assess all event terms (AEs) for toxicity grade, or severity, regardless of whether the event is transfusion-related (HHS-2010). AEs will also be presented by maximum severity or maximum common terminology criteria for AE (CTCAE) grade (depending on collection). A summary of SAEs and a summary of AEs leading to treatment discontinuation will be presented.

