# 10.1. Specification of Safety Endpoints

The investigator will review subjects' medical records and administer a focused review of systems and a physical examination to all subjects to determine the presence of symptoms or signs of coagulation abnormalities.

Primary safety endpoints will include those related to vital signs, clinical laboratory parameters (chemistry, hematology, urine analysis, and coagulation), and AEs.

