# 11.4. Interim Analysis and Stopping Rules

The SRs for the study are presented in section 6.5. No interim analysis is planned for this study.

At the conclusion of each cohort and after Cohort 3 study activities, the DSMB will review all patient safety data and make a recommendation to the sponsor on whether to proceed with dose escalation in the subsequent cohort and after cohort 3 with the next planned FDP trial protocol as mentioned in section 11.1. No adjustment for multiple testing is necessary since no statistical hypotheses are being tested. (The planned descriptive analyses are described in section 11.1.)

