^a=Denominator for each % is the treatment group N.

^b=Denominator adjusted because gender-specific event for males: N=XX (FDP-CPD), N=XX (FDP-ACD) for Cohort 1; N=XX (FDP-CPD), N=XX (FDP-ACD) for Cohort 2; N=XX (A), N=XX (B) for Cohort 3 [for applicable PTs].

^c=Denominator adjusted because gender-specific event for females: N=XX (FDP-CPD), N=XX (FDP-ACD) for Cohort 1; N=XX (FDP-CPD), N=XX (FDP-ACD) for Cohort 2; N=XX (A), N=XX (B) for Cohort 3 [for applicable PTs].

Preferred Terms within System Organ Class are sorted in descending order of frequency based on the treatment-emergent adverse event category.

Table 7.4. - Table 7.6 . Summary of Suspected Unexpected Serious Adverse Reactions (SUSARs)

**Subject Incidence of SUSARs
 Safety Population – S1 (N=XX)**

**FDP-1
 Phase I**

	Cohort 1		Cohort 2		Cohort 3	
Preferred Term	FDP-CPD 270 mL (N = XX) n (% ^a)	FDP-ACD 270 mL (N = XX) n (% ^a)	FDP-CPD 540 mL (N = XX) n (% ^a)	FDP-ACD 540 mL (N = XX) n (% ^a)	FDP-ACD X FFP 810 mL (N = XX) n (% ^a)	FFP X FDP- ACD 810 mL (N = XX) n (% ^a)
Number of subjects reporting serious adverse events	xx (xx.x)	xx (xx.x)				
	xx (xx.x)	xx (xx.x)				
[Preferred Term #1]	xx (xx.x)	xx (xx.x)				
[Preferred Term #2] ^{b,c}	xx (xx.x)	xx (xx.x)				
....	xx (xx.x)	xx (xx.x)				

Programming Note: This table will not be produced until final data analysis. This table will be repeated for all safety analysis populations that are determined to be on a different set of subjects as described in Section 4.2 for each cohort (Table 7.5- Table 7.6). All tables may not be produced based on the table reduction method mentioned in Section 4.2 and may not exactly match the SAP. The titles for the tables will be the same for the other populations with the name of the population changing based on the population being used.

Special Note: For Cohort 3, there will be an Open and Closed session for the DSMB. For the Open session only for Cohort 3, an overall total column will be shown with the table numbers having the word “(Open)” after the decimal as shown above. Footnotes for

Notes: Subjects are counted at most once on each row. Subjects may be included on more than one row.

^a=Denominator for each % is the treatment group N.

^b=Denominator adjusted because gender-specific event for males: N=XX (FDP-CPD), N=XX (FDP-ACD) for Cohort 1; N=XX (FDP-CPD), N=XX (FDP-ACD) for Cohort 2; N=XX (A), N=XX (B) for Cohort 3 [for applicable PTs].

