Notes: Subjects are counted at most once on each row. Subjects may be included on more than one row.

^a=Denominator for each % is the treatment group N.

^b=Denominator adjusted because gender-specific event for males: N=XX (FDP-CPD), N=XX (FDP-ACD) for Cohort 1; N=XX (FDP-CPD), N=XX (FDP-ACD) for Cohort 2; N=XX (A), N=XX (B) for Cohort 3 [for applicable PTs].

^c=Denominator adjusted because gender-specific event for females: N=XX (FDP-CPD), N=XX (FDP-ACD) for Cohort 1; N=XX (FDP-CPD), N=XX (FDP-ACD) for Cohort 2; N=XX (A), N=XX (B) for Cohort 3 [for applicable PTs].

Preferred Terms within System Organ Class are sorted in descending order of frequency based on the treatment-emergent adverse event category.

Table 9.1. - Table 9.146. XX Measures (Units) Change from Baseline Over Time (Since Treatment Emergent Change)
XX Measures (Units) Change from Baseline Over Time (Since Treatment Emergent Change) – Cohort 1 (270 mL)
Safety Population – S3 (N=XX)

FDP-1
Phase I

	Pre-Infusion		Post-Infusion			Follow-Up Visit		
			Change from Baseline to 30 Minutes		Change from Baseline to 4 Hours		Change from Baseline to 24 Hours	
Treatment	FDP-CPD	FDP - ACD	FDP-CPD	FDP-ACD	FDP-CPD	FDP-ACD	FDP-CPD	FDP-ACD
N	xx	xx	xx	xx	xx	xx	xx	xx
Mean	xx.xx	xx.xx	xx.xx	xx.xx	xx.xx	xx.xx	xx.xx	xx.xx
SD	xx.xx	xx.xx	xx.xx	xx.xx	xx.xx	xx.xx	xx.xx	xx.xx
Min	xx.xx	xx.xx	xx.xx	xx.xx	xx.xx	xx.xx	xx.xx	xx.xx
Q1	xx.xx	xx.xx	xx.xx	xx.xx	xx.xx	xx.xx	xx.xx	xx.xx
Median	xx.xx	xx.xx	xx.xx	xx.xx	xx.xx	xx.xx	xx.xx	xx.xx
Q3	xx.xx	xx.xx	xx.xx	xx.xx	xx.xx	xx.xx	xx.xx	xx.xx
Max	xx.xx	xx.xx	xx.xx	xx.xx	xx.xx	xx.xx	xx.xx	xx.xx
>ULN ^a	xx (x.x)	xx (x.x)	xx (x.x)	xx (x.x)	xx (x.x)	xx (x.x)	xx (x.x)	xx (x.x)

Programming Note: This table has been restricted to the time points pre-infusion, 30 minutes and 4 hours post infusion at the request of the investigator, except for the hematology variables where pre-infusion, 30 minutes, 4 hours, and 24 hours will be shown. This table will be generated in the S3 population only. This table will be produced for the following endpoints where data is available:

- Vital Signs:
 - Blood Pressure (mmHg)
 - Table 9.1 (Diastolic Blood Pressure (mmHg))
 - Table 9.2 (Systolic Blood Pressure (mmHg))
 - Heart Rate (beats/min) (Table 9.3)

Note: ^a=Denominator for each % is the treatment group N at each individual time point

- Respiration Rate (breaths/min) (Table 9.4)
- Temperature (°F) (Table 9.5)
- Hematology:
 - Hematocrit (%) (Table 9.6)
 - Hemoglobin (g/dL) (Table 9.7)

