XX Measures (Units) Change from Baseline Over Time Since Treatment Emergent Change – Cohort 2 (540 mL)
Safety Population – S3 (N=XX)
FDP-1
Phase I

Programming Note: For Cohort 3, the treatment arms will be unmasked for final data analysis once the study has been unblinded. This table will also be repeated for Cohort 3 for the first infusion:

- Vital Signs:
 - Blood Pressure (mmHg)
 - Table 9.61 (Diastolic Blood Pressure (mmHg))
 - Table 9.62 (Systolic Blood Pressure (mmHg))
 - Heart Rate (beats/min) (Table 9.63)
 - Respiration Rate (breaths/min) (Table 9.64)
 - Temperature (°F) (Table 9.65)
- Hematology:
 - Hematocrit (%) (Table 9.66)
 - Hemoglobin (g/dL) (Table 9.67)
 - Platelet Count (10⁹/L) (Table 9.68)
 - RBC Count (10¹²/L) (Table 9.69)
 - WBC Count (10⁹/L) (Table 9.70)
- Clinical Chemistry:
 - ALP (U/L) (Table 9.71)
 - ALT (U/L) (Table 9.72)
 - AST (U/L) (Table 9.73)
 - Ionized Calcium (mg/dL) (Table 9.74)
 - Total Magnesium (mg/dL) (Table 9.75)
 - Serum pH (Table 9.76)
 - Calcium (mg/dL) (Table 9.77)
 - Chloride (mmol/L) (Table 9.78)
 - Potassium (mmol/L) (Table 9.79)

Note: ^a=Denominator for each % is the treatment group N at each individual time point

73

Program Path:

Data source: ADVS, ADLB Cross Reference: Listing 10-12, Listing 20-23, Listing 26-27

Data extract date:

- Sodium (mmol/L) (Table 9.80)
- Lactic Acid (mmol/L) (Table 9.81)
- Bicarbonate (mmol/L) (Table 9.82)
- Glucose (mg/dL) (Table 9.83)
- Total Bilirubin (mg/dL) (Table 9.84)
- Total Protein (g/dL) (Table 9.85)
- BUN (mg/dL) (Table 9.86)
- Creatinine (mg/dL) (Table 9.87)
- Coagulation Factor Tests (All Cohorts):
 - PT (sec) (Table 9.88)
 - INR (Table 9.89)
 - aPTT (sec) (Table 9.90)
- Coagulation Factor Tests (Cohort 3 only):
 - Factor I (mg/dL) (Table 9.91)
 - Factor II (% Normal) (Table 9.92)
 - Factor V (% Normal) (Table 9.93)
 - Factor VII (% Normal) (Table 9.94)
 - Factor VIII (% Normal) (Table 9.95)
 - Factor IX (% Normal) (Table 9.96)
 - Factor X (% Normal) (Table 9.97)
 - Factor XI (% Normal) (Table 9.98)
 - von Willebrand Factor Activity (%) (Table 9.99)
 - Protein C (Factor XIV Activity) (% Normal) (Table 9.100)
 - Protein S (% Normal) (Table 9.101)
 - Antithrombin III (% Normal) (Table 9.102)
 - Alpha-2 Antiplasmin (% Normal) (Table 9.103)

The title for Cohort 3 for the first infusion is shown below:

**Table XX.XX Measures (Units) Change from Baseline Over Time Since Treatment Emergent Change

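### The SAP's list of DSMB outputs holds only demographics, disposition and adverse events, which conflicts with the board's stated remit to review all safety data before each dose step

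*SAP*

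**What the plan says.** SAP 4.5.3 sets out what is produced for the board's formal safety reports: "analyses required to generate Table 1.1 – Table 8.3 and Figures 1 and 2 will be conducted as prescribed in the FDP-1 DSMB Charter". The sentence ends by removing the SUSAR tables (7.4-7.6). For Cohort 3 the same section plans Open tables (totals) and Closed tables (masked A and B).

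Other sections describe a wider review. Protocol 11.4 says that, as each cohort ends, "the DSMB will review all patient safety data and make a recommendation to the sponsor on whether to proceed with dose escalation". Protocol 11.1 refers to all subjects' cumulative safety data. Protocol 6.5 sets a minimum of all data through the 7-day visit, and SAP 1.1 sets a minimum of complete subject data through that visit.

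On what counts as safety data, Protocol 11.1 says safety is assessed through vital signs, laboratory tests during and after infusion, and product-related adverse events. Protocol 10.1 states: "Primary safety endpoints will include those related to vital signs, clinical laboratory parameters (chemistry, hematology, urine analysis, and coagulation), and AEs".

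The programming note under Tables 7.4-7.6 says "This table will not be produced until final data analysis". The special note beneath it says "For Cohort 3, there will be an Open and Closed session for the DSMB" and describes both versions.

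**The concern.** The product had never been infused into humans (Protocol 5.5.2.1). The risks named in Protocol 5.6.1.4 include citrate toxicity with hypocalcemia, circulatory overload and coagulopathy. Such effects can show in laboratory values and vital signs without being recorded as adverse events.

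Stopping rule 4 is triggered by one subject's PT/INR or aPTT result that is both abnormal and more than 20% from baseline. No rule in the documents makes a smaller change in aPTT, D-dimer or ionized calcium an adverse event. A consistent shift across a cohort that stays below that threshold would appear in none of the tables that SAP 4.5.3 lists. The board uses that report to advise on going from about 270 to 540 mL (a doubling) and then from 540 to 810 mL (810/540 = 1.5, a 50% increase). After Cohort 3 it advises on the next trial.

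**Working it through.** The plan gives no figure for the contents of the board's report, so the check maps every numbered table in SAP section 5 to the range in SAP 4.5.3 and counts. Open and Closed versions count once. The numbering is taken in full, before the table-reduction rule in SAP 4.2.2.

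**Listed for the board**

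| Tables | Content | Number |
|---|---|---|
| 1.1-1.21 | Demographics, disposition | 21 |
| 2.1-2.20 | AE overview | 20 |
| 3.1-3.12 | TEAEs by preferred term | 12 |
| 4.1-4.9, 5.1-5.9, 6.1-6.9 | TEAEs by relatedness, severity, CTCAE grade | 27 |
| 7.1-7.3 | SAEs | 3 |
| 8.1-8.3 | AEs leading to discontinuation | 3 |

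Total: 21 + 20 + 12 + 27 + 3 + 3 = 86. Figures 1 and 2 show disposition.

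**Not listed**

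| Tables | Content | Number |
|---|---|---|
| 7.4-7.6 | SUSARs (excluded by name) | 3 |
| 9.1-9.146 | Vital signs, hematology, chemistry, PT/INR/aPTT, factors | 146 |
| 10.1-10.36 | Urinalysis, DAT | 36 |
| 11.1-11.34 | PT/INR/aPTT and D-dimer shifts; for Cohort 3 also PF 1+2, TAT, C3a des Arg | 34 |
| 12.1-12.38 | Cohort 3 by sequence and period | 38 |
| 13.1-13.2 | Cohort 3 pre-infusion DAT | 2 |
| 14 | Exposure | 1 |

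Total: 3 + 146 + 36 + 34 + 38 + 2 + 1 = 260, of which 257 hold measurements or exposure.

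**Size at each escalation decision.** For Cohort 1 the unlisted tables are 9.1-9.30 (30), 10.1-10.9 (9), the four high-shift tables 11.1-11.4, and three low-shift tables. The low-shift set 11.23-11.34 has 12 tables: 3 assays × 4 sets (Cohort 1, Cohort 2 and the two Cohort 3 infusions). So 30 + 9 + 4 + 3 = 46. Cohort 2 also has 46, giving 92 for the two decisions. Exposure Table 14 comes on top.

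**Would adding the tables be enough?** Not by themselves, for three reasons.

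- Tables 9 to 11 use the S3 population, which requires the full dose and the 7-day visit (SAP 4.2.2). A subject whose infusion was cut short drops out.
- Table 10 shows pre-infusion, 30 minutes and 4 hours. Protocol Tables 7 and 9 schedule post-infusion DAT at 24 hours and day 28 only, although the text of Protocol 8.2.2 lists it earlier for Cohort 3. For Cohorts 1 and 2 the DAT tables would therefore show no post-infusion result.
- Day-7 chemistry and CBC are drawn, but Table 9 has no day-7 column.

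The existing listings can fill all three gaps: exposure (8), vital signs (10-12), hematology, chemistry, urinalysis, coagulation and DAT (20-30).

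**The case against.** **The charter may supply the data.** SAP 4.5.3 defers to the DSMB charter, and Protocol section 10 and SAP 3.5 place the reporting requirements there. SAP 4.5.3 does not say that only the listed tables go to the board. SAP 1.1 promises complete subject data, and the listings exist. This stands. A reader might infer that the board advises on escalation without seeing any vital sign or laboratory result; the documents do not support that. They show only that the SAP plans no such output for the board and contradicts its own promise.

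**The primary endpoints are adverse events.** Protocol 6.4.1 and 11.1.1 and SAP 4.5.3.1 list TEAEs, SAEs, SUSARs and deaths. Protocol 6.1 rests the safety conclusion on TEAEs alone, and Protocol 6.4.2 makes laboratory and vital sign changes secondary, for Cohort 3 only. That describes the final conclusion fairly. It does not narrow the board's remit, which Protocol 11.1 and 11.4 put as all safety data.

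**Other safeguards act on individual data.** The stopping rules apply throughout. The research monitor reviews the first 5 of 8 subjects per cohort through 24 hours before the next infusion (Protocol Appendix A). The PI reviews post-infusion D-dimer before release, and acute reactions are specifically documented (Protocol 10.5.1). These reduce the risk. None is a cohort-level summary for the board.

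**SUSARs.** A reader might infer that serious reactions are kept from the board. They are not: SAE Tables 7.1-7.3 are in the package, a related SAE pauses the study, and the pharmacovigilance physician assesses reporting to the FDA and DSMB. What remains is the conflict between the exclusion, "as prescribed in the FDP-1 DSMB Charter, except for Tables 7.4-7.6", and the Open and Closed versions described under those tables.

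**Timing notes.** The note "For Cohort 3, the treatment arms will be unmasked for final data analysis once the study has been unblinded" might be read as holding Tables 9 to 14 back until the end. It concerns the unmasking of Cohort 3 arms. For Cohorts 1 and 2 the omission rests on SAP 4.5.3 alone.

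**Conclusion.** The contradiction between SAP 4.5.3 and Protocol 6.5, 11.1 and 11.4 and SAP 1.1 is real. As specified, the board's report has 86 tables on demographics, disposition and adverse events, and none on vital signs, laboratory values, coagulation, D-dimer, DAT or exposure. For each of the two escalation decisions, 46 specified tables for the cohort just completed, plus the exposure table, are not listed. The count measures missing content, not the probability of missing a signal.

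The conclusion rests on the SAP and protocol as they stand. If the charter already sends these data to the board, the defect reduces to a missing cross-reference. If it does not, each escalation recommendation would rest on less than the protocol says it does. Either way the texts should be reconciled before a cohort review relies on them.

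**What to change.** 1. In SAP 4.5.3, add Tables 9, 10, 11 and 14 to the DSMB set for each cohort review. Cohorts 1 and 2 are unmasked, so their tables can go as they are. For Cohort 3, produce Open (total) and Closed (A/B) versions, as for Tables 1 to 8. Table 12 rearranges Cohort 3 measurements already in Table 9, and Table 13 holds only pre-infusion DAT, so neither is essential for the board.
2. Also supply Listings 8, 10-12 and 20-30 for all infused subjects (S1). The listing shells name no population, so state it. For Cohort 3, mask the arm header and the product names. With four subjects per arm, listings are practical, and they cover partial infusions, 24-hour DAT and day-7 results.
3. Reconcile SAP 4.5.3 with the charter, and cite the charter section if it already provides any of these outputs.
4. Reconcile the exclusion of Tables 7.4-7.6 with the note beneath them, for example by giving the board the sponsor safety office's current SUSAR listing at each meeting. SAP 4.5.3 already expects a listing from that office; only its timing needs to change.

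The cost is SAP wording, earlier programming of outputs already specified, masked Cohort 3 versions, and a longer report. No new data are needed.
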